	 Non-hematologic DLT: Liver Any grade 3 AST/ALT that does not resolve to grade 1 within 14 days or any grade 4 elevation in liver function tests (AST/ALT) Gastrointestinal Grade 3 vomiting or nausea despite the use of standard antiemetics Grade 3 diarrhea or constipation despite the use of optimal treatment All other events Grade 3 (excluding hypersensitivity reactions and fatigue) Hematologic DLT: Grade 4 thrombocytopenia that requires more than one platelet transfusion and does not resolve to grade 2 or less within 14 days Grade 4 neutropenia that does not resolve to grade 2 or less within 14 days or any other grade 4 hematologic toxicities that do not resolve to grade 2 or less within 14 days or any other grade 4 hematologic toxicities that do not resolve to grade 2 or less within 14 days or any other grade 4 hematologic toxicities that do not resolve to grade 2 or less within 14 days or any other grade 4 hematologic toxicities that do not resolve to grade 2 or less within 14 days or any other grade 4 hematologic toxicities that are considered clinically relevant by the investigator Any AE that delays treatment with study drug for more than 14 days In addition, any event will only qualify as a DLT if a worsening of the event from baseline of at least 2 CTCAE Grades occurs. The DLTs for the POM combination cohorts are specified as above except for the hematological DLTs which are as follows: Hematologic DLT: Grade 4 neutropenia for > 7 days

	Parts A, B, C: MOR03087
Pharmacokinetics	Concentration-time profiles and pharmacokinetic parameters of MOR03087 +/- LEN or POM will be assessed from samples collected on the following schedules (if not otherwise specified, a deviation of 5 minutes from the planned collection time point will be acceptable):
Subject-Reported Outcomes/Quality of Life	Quality of life will be evaluated using the QLQ-30 and the QLQ-MY20, an instrument for use in subjects with MM.
	Subjects experiencing DLTs should not receive further study drug. A pharmacokinetic interim analysis may be performed at any time during dose escalation if unexpected MOR03087 serum concentration results are observed.
	The DLT period covers Day 1 of cycle 1 (starting with first study drug administration) until Day 29 (before start of the second cycle).

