# 8.5 Dose Limiting Toxicities

Adverse events will be graded according to NCI CTCAE, version 4.0, with a DLT being defined as an AE assessed as having a suspected or unknown relationship to the study drug (MOR03087, POM, or LEN) and meeting one of the following criteria:

- Non-hematologic DLT:
  - o Liver

Any grade 3 AST/ALT that does not resolve to grade 1 within 14 days or any grade 4 elevation in liver function tests (AST/ALT)

- Gastrointestinal
  - $\geq$  Grade 3 vomiting or nausea despite the use of standard antiemetics

Sponsor: MorphoSys AG

- $\geq$  Grade 3 diarrhea or constipation despite the use of optimal treatment
- All other events
  - ≥ Grade 3 (excluding hypersensitivity reactions and fatigue)
- Hematologic DLT:
  - Grade 4 thrombocytopenia that requires more than one platelet transfusion and does not resolve to grade 2 or less within 14 days
  - Grade 4 neutropenia that does not resolve to grade 2 or less within 14 days
  - Or any other grade 4 hematologic toxicities that do not resolve to grade 2 or less within 14 days and that are considered clinically relevant by the investigator
- Any AE that delays treatment with study drug for more than 14 days

In addition, any event will only qualify as a DLT if a worsening of the event from baseline of at least 2 CTCAE Grades occurs.

The DLTs for the POM combination cohorts are specified as above except for the hematological DLTs which are as follows:

- Hematologic DLT:
  - Grade 4 neutropenia for > 7 days
  - Febrile neutropenia (ANC <1000/mm³ with a single temperature of >38.3°C or a sustained temperature of  $\geq$  38°C for more than 1 hour)
  - o Thrombocytopenia
    - Platelet count  $< 25,000/\mu$ L that requires more than one platelet transfusion or
    - Platelet count  $\ge 25,000/\mu L$  to  $< 50,000/\mu L$  with significant bleeding (defined as need for hospitalization and/or platelet transfusion)
  - Or any other grade 4 hematologic toxicities that do not resolve to grade 2 or less within 14 days and that are considered clinically relevant by the investigator

The DLTs for the LEN combination cohorts are specified as above except for the hematological DLTs which are as follows:

- Hematologic DLT:
  - Grade 4 neutropenia for > 7 days
  - Febrile neutropenia (ANC <1000/mm³ with a single temperature of >38.3 °C or a sustained temperature of  $\geq$  38 °C for more than 1 hour)
  - o Thrombocytopenia

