    - Platelet count  $< 30,000/\mu$ L that requires more than one platelet transfusion or
    - Platelet count  $\ge$  30,000/µL to < 50,000/µL with significant bleeding (defined as need for hospitalization and/or platelet transfusion)
  - Or any other grade 4 hematologic toxicities that do not resolve to grade 2 or less within 14 days and that are considered clinically relevant by the investigator

The DLT period covers Day 1 of cycle 1 (starting with first study drug administration) until Day 29 (before start of the second cycle). Granulocyte-colony stimulating factor (GCSF) therapy is prohibited during this time.

Laboratory DLTs will be reported as AEs.

Sponsor: MorphoSys AG

Confidential

Subjects experiencing DLTs in the study should not receive further study drug.

If upon treatment with POM or LEN, subjects present with protocol-defined DLTs or toxicities or conditions described in the corresponding Section 9.1.4, treatment must be modified or interrupted accordingly.

If upon treatment with DEX, subjects present with protocol-defined toxicities or conditions described in the corresponding SmPC, treatment must be modified or interrupted accordingly.

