#### Table 5LEN Dose Modification Instructions for Toxicities

Toxicity	LEN Dose Modification
Neutropenia (ANC < 0.5 x 10 ⁹ /L)	Stop LEN dosing and follow hematology weekly. If the subject was not receiving GCSF therapy, GCSF therapy may be started at the discretion of the treating physician. When ANC returns to $\geq 0.5 \times 10^{9}$ /L, LEN dosing may be restarted at same dose level if neutropenia was the only DLT and GCSF treatments are continued, or decreased by one dose level. Note: GCSF is prohibited during Cycle 1
Thrombocytopenia (Platelets <30 x10 ⁹ /L)	Stop LEN dosing and follow hematology weekly. When platelets return to $\geq 30 \times 10^9$ /L, resume LEN dosing at one dose level lower

Toxicity	LEN Dose Modification
Rash	
 
Grade 2-3 skin rash: LEN interruption or discontinuation should be considered at the discretion of the treating physician.
 
Angioedema, Grade 4 rash, exfoliative or bullous rash or if Stevens-Johnson syndrome (SJS) or toxic epidermal necrolysis is suspected, LEN must be discontinued permanently
 

Other $\geq$ Grade 3 LEN-related adverse events	Stop LEN dosing and restart at one dose level lower when toxicity has resolved to $\leq$ Grade 2 at physician's discretion.

ANC: absolute neutrophil count; DLT: dose limiting toxicity; GCSF: granulocyte colony-stimulating factor; LEN: lenalidomide

LEN should be discontinued if the subject is unable to tolerate the lowest dose level. At the discretion of the investigator, the treatment with MOR03087 and dexamethasone may be continued.

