# 9.1.4.2 POM Dose Modification

Subjects will be evaluated for AEs at each visit with the NCI CTCAE version 4.0 as a guide for the grading. Interruptions and reductions are permitted throughout the study.

Table 6 outlines the dose reduction steps for POM. Instructions for dose interruptions and reductions for POM are outlined in Table 7 (hematologic and non-hematologic toxicities).

Table 6Pomalidomide Dose Reduction Steps by Dose Level

Dose Level (Days 1-21 of 28 days)	POM Dose Reduction (Days 1-21 of Every 28-Day Cycle)
Starting dose	4 mg
Dose Level -1	3 mg
Dose Level -2	2 mg
Dose Level -3	1 mg ¹

POM: pomalidomide

¹ The POM treatment regimen should be discontinued if the subject cannot tolerate the 1 mg dose.

Table 7	Pomalidomide Dose Modification Instructions for Toxicities

Toxicity	POM Dose Modification
Neutropenia ANC < $0.5 \ge 10^{9}$ /L) or Febrile neutropenia (fever $\ge 38.5$ °C and ANC < $1.0 \ge 10^{9}$ /L)	Hold POM dosing and follow hematology weekly. If the subject was not receiving GCSF therapy, GCSF therapy may be started at the discretion of the treating physician. When ANC returns to $\geq 0.5 \ge 10^{9}$ /L, restart POM dosing at one dose level lower. Note: GCSF is prohibited during Cycle 1
Thrombocytopenia (Platelets < 25 x 10 ⁹ /L)	Hold POM dosing and follow hematology weekly. POM dosing may resume at one dose level lower once the platelet count has recovered to $\geq 50,000/\mu$ L.
Other $\geq$ Grade 3 POM-related toxicities	Interrupt POM dosing and restart at one dose level lower when toxicity has resolved to $\leq$ Grade 2 at the physician's discretion

ANC: absolute neutrophil count; GCSF: granulocyte colony-stimulating factor; POM: pomalidomide

To initiate a new cycle of POM, the neutrophil count must be  $\ge 0.5 \ge 10^9/L$  with or without GCSF, the platelet count must be  $\ge 50 \ge 10^9/L$ .

POM should be discontinued if subject is unable to tolerate the lowest dose level. At the discretion of the investigator, the treatment with MOR03087 and dexamethasone may be continued.

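### After a DLT in Parts D and E, the protocol both bars further study drug and directs that lenalidomide or pomalidomide be modified, interrupted and possibly restarted

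*Protocol*

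**What the plan says.** **The stop rule.** Protocol 8.5: "Subjects experiencing DLTs in the study should not receive further study drug". The synopsis has the same rule: "Subjects experiencing DLTs should not receive further study drug". Neither place gives an exception.

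**What study drug means here.** Section 8.5 defines a DLT as an AE with a "suspected or unknown relationship to the study drug (MOR03087, POM, or LEN") that also meets one of the listed criteria.

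**The competing rule.** The paragraph of 8.5 that follows the stop rule covers subjects treated with POM or LEN: if "subjects present with protocol-defined DLTs or toxicities or conditions described in the corresponding Section 9.1.4, treatment must be modified or interrupted accordingly".

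**What Section 9.1.4 then allows.** For neutropenia on LEN, Table 5 says "LEN dosing may be restarted at same dose level if neutropenia was the only DLT and GCSF treatments are continued"; the alternative it gives is a reduction by one dose level. For neutropenia or febrile neutropenia on POM, Table 7 says to hold dosing and, once the neutrophil count recovers, "restart POM dosing at one dose level lower". Both tables also provide for restart one level lower after other LEN- or POM-related toxicity of Grade 3 or higher.

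**The window.** Section 8.5 sets the DLT period as Cycle 1 Day 1 to Day 29, before Cycle 2, and prohibits GCSF during it.

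**The concern.** A site treating a Part D or E subject who has just had a DLT can find two instructions a paragraph apart. One ends study drug. The other keeps POM or LEN under a modify-or-interrupt scheme that leads to restart rules. Two sites with identical subjects could act in opposite ways and each cite the protocol.

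In a dose-finding trial this is first a matter of patient safety: whether a subject is re-exposed after a dose-limiting event should not depend on which paragraph is read. It is secondarily a matter of data. What is recorded after a DLT (exposure, later AEs, time to treatment discontinuation) would follow the instruction chosen rather than a common rule, in cohorts of three to six subjects.

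**Working it through.** No calculation decides this. The check is a comparison of texts, followed by a look at which analyses depend on the answer.

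**1. Can the stop rule be read as MOR03087 only?** That reading would remove the conflict. But Section 8.5 lists MOR03087, POM and LEN as the study drug; Section 11.3.4 uses the same list; Table 2 labels the LEN and POM capsules as study drug administration; and SAP 7.3.6 counts all the agents as study drugs. Nothing restricts the stop rule to the antibody.

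**2. Do the two rules apply at the same time?** Yes. Sections 9.1.4.1 and 9.1.4.2 allow interruptions and reductions at any point in the study. Tables 5 and 7 both carry a reminder about GCSF in Cycle 1, so they were written with that cycle in view.

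**3. Do they apply to the same events?** The criteria overlap once units are matched: 1000/mm³ = 1.0 × 10⁹/L, 30,000/µL = 30 × 10⁹/L and 25,000/µL = 25 × 10⁹/L.

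| Event in Cycle 1 | DLT under 8.5 | Section 9.1.4 |
|---|---|---|
| Febrile neutropenia, Part D | ANC under 1000/mm³ and one reading above 38.3 °C (or 38 °C or more for over an hour) | Table 7: ANC under 1.0 × 10⁹/L, fever 38.5 °C or more; hold, restart one level down |
| Low platelets, Part D | Under 25,000/µL with more than one transfusion | Table 7: under 25 × 10⁹/L; hold, may resume one level down |
| Low platelets, Part E | Under 30,000/µL with more than one transfusion | Table 5: under 30 × 10⁹/L; stop, resume one level down |
| Other Grade 3 or higher | DLT, apart from hypersensitivity and fatigue | Tables 5 and 7: if LEN- or POM-related, restart one level down after resolution |

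Example: a POM subject with ANC under 1.0 × 10⁹/L and a temperature of 38.6 °C exceeds both fever limits (38.6 > 38.3 and 38.6 ≥ 38.5). If the event is drug-related and the required two-grade worsening from baseline is met, 8.5 bars further study drug while Table 7 restarts POM.

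For LEN no overlap argument is needed, because Table 5 itself uses the term DLT when permitting restart. For POM, the text of 8.5 expressly links a DLT to modification or interruption, and restart follows from the overlap with Table 7.

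**4. Does another section settle it?** No. The DLT Evaluable Population (Protocol 15.1, SAP 6) excludes subjects with a Cycle 1 LEN or POM modification only when it is unrelated to a DLT. That wording contemplates a DLT-related modification and gives no order of precedence.

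**5. What in the analysis depends on it?**
- Exposure: SAP 7.3.6 derives treatment duration, LEN and POM dose reductions, and LEN or POM discontinuation with MOR03087 continued.
- Later AEs: under SAP 10.2 the treatment-emergent window and the time at risk for exposure-adjusted rates run to 28 days after last study treatment.
- EFS: SAP 7.3.3.3 counts discontinuation for any reason as an event. Under the stop rule the DLT subject has an EFS event when treatment stops; under restart there is none until progression, death or a later stop.

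**6. How many subjects could meet the conflict?** The synopsis allows up to 18 subjects in each of Parts D and E: 18 + 18 = 36, out of 48 + 18 + 24 + 18 + 18 = 126. That is a ceiling on subjects governed by both rules, not a forecast of DLTs.

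**The case against.** The strongest defence is that Table 5 uses DLT loosely for any later LEN toxicity. The same cell notes the Cycle 1 ban on GCSF, GCSF is allowed from Day 29 (Section 9.4), and Protocol 15.7.1 speaks of summarising DLTs in further cycles, although SAP 10.1 limits DLT summaries to Cycle 1. This reading is plausible for Table 5. It does not help with 8.5, where the modify-or-interrupt sentence refers to protocol-defined DLTs, and the body's stop rule covers DLTs occurring at any time in the study.

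It also means that a reader who infers a separate GCSF conflict goes too far. The cell carries its own Cycle 1 limit, and GCSF could begin on Day 29. What remains is a question of terminology.

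Not every DLT opens the restart route. A DLT attributed only to MOR03087 does not meet the LEN- or POM-related rows for other toxicities, and for a delay of more than 14 days Section 8.6 already requires permanent discontinuation. This narrows the point without removing it.

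Oversight is also real. DLTs are reportable within 24 hours (Section 12.1) and deviations go to the medical monitor (Section 16.3.5). That makes divergent handling easier to detect, but it does not tell the site or the monitor which instruction applies.

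Finally, the SAP already provides exposure variables and a DLT listing from which post-DLT treatment can be reconstructed, so a dedicated SAP flag is a convenience.

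**Conclusion.** The protocol is wrong as written. For a Part D or E subject with a DLT it contains two incompatible instructions, and no text ranks them. The conclusion rests on reading study drug as Section 8.5 itself lists it and, for POM, on the overlap between DLT criteria and Table 7.

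Three stronger inferences are not supported:
- **That the dose-finding result is at risk.** The first DLT is counted before any decision on further treatment, DLT withdrawals stay in the DLT Evaluable Population and are not replaced, and sponsor or DMC classification overrides the site's (SAP 10.1). The 3+3 decision and the MTD do not change.
- **That PFS becomes site-dependent.** SAP 7.3.3.3 defines it by progression or death, and subjects who stop without progression are followed every 4 weeks. Only an indirect effect through treatment itself is possible.
- **That a given number of subjects per recommended-dose group is affected.** The documents state no DLT rate. Two DLTs in six subjects (33%) already places the MTD one level lower (SAP 10.1), so that figure cannot serve as the rate expected at a recommended dose.

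EFS is affected, but it is an additional descriptive variable, not a listed secondary endpoint. The main weight of the point is subject safety and consistent handling.

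**What to change.** Reconcile the synopsis, Section 8.5, Table 5 and Table 7 into one instruction stating which agents, if any, may continue after a DLT, and use the same words in each place. Align Table 5's use of DLT with the Cycle 1 window in 8.5, so that it is clear whether the cell means a protocol-defined DLT or some other toxicity. Which clinical rule to adopt is for the sponsor and its clinical advisers; this review offers no view.

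Section 13.1 requires changes by amendment, so the cost is a protocol clarification. It alters no sample size, visit schedule or planned analysis. Optionally, the SAP could mark post-DLT LEN or POM exposure as permitted or as a deviation in the existing DLT listing, using data already collected.

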# 8.6 Other Reasons for Treatment Postponement

Study drug administration may be delayed for medical or other reasons (e.g., social reasons, weather circumstances). In case of a delay in study drug administration, the treatment should be restarted as early as possible. Should treatment be delayed for more than 14 days after the missed dose, then the treatment should be permanently discontinued. The subject should continue with the first follow-up visit in the study.

# 8.7 Withdrawal and Termination Criteria

# 8.7.1 Subject Withdrawal

In accordance with the current version of the Declaration of Helsinki and the European Parliament and Council Directive 2001/20/EC in its current version, each subject is free to withdraw from the study at any time without giving any reason for his or her decision. Investigators also have the right to withdraw subjects from the study in the event of illness, AEs, or other reasons concerning the health or well-being of the subject, or in the case of lack of cooperation and/or protocol non-compliance.

Should the investigator decide to discontinue Investigational Medicinal Product (IMP) administration for a specific subject during the treatment period in the event of illness, AEs, or other reasons concerning the health or well-being of the subject, then the subject will be allowed to complete the follow-up visits in accordance with the protocol.

Should a subject decide to withdraw after administration of the IMP, or should the investigators decide to withdraw the subject, all efforts should be made to complete and report the observations up to the time of withdrawal as thoroughly as possible. A complete final evaluation at the time of the subject's withdrawal (End of Study visit) should be made.

During the conduct of the study, the sponsor will also review the safety data for trends and signals that would indicate the need for withdrawal of a subject or subjects.

If available, the reason for withdrawal should be noted in the electronic Case Report Form (eCRF). If the reason for withdrawal is an AE, monitoring will continue until the outcome is evident (provided that the reason for withdrawal is not "withdraw consent"). The specific event or test result(s) must be recorded in the eCRF.

Subjects may withdraw or may be withdrawn from the study for the following reasons:

- A subject is significantly non-compliant with the requirements of the protocol (e.g., a subject who takes prohibited concomitant medications for a consistent period that, in the investigator's opinion, would interfere with the interpretation of the study data).
- A subject becomes pregnant.
- A subject has an AE that would, in the investigator's judgment, make continued participation in the study an unacceptable risk.
- The sponsor decides to discontinue the study.
- A subject withdraws at his or her own request (withdrawal of consent).
- A subject has major protocol violations.
- A subject is withdrawn at the specific request of the sponsor in case of serious safety concerns.
- A subject is treated with another monoclonal antibody.
- A subject requires different myeloma-specific treatment due to progressive disease.

Subjects who receive specific anti-myeloma treatment other than those specified in the protocol should be withdrawn from the study.

Subjects who withdraw whilst their safety assessment period is not evaluable will only be replaced during the dose-escalation phase until the applicable cohort consists of a sufficient number of evaluable subjects. However, withdrawals due to DLTs will not be replaced.

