¹ A follow-up visit will be repeated every fourth week (± 2 days) until progressive disease, or receipt of new anti-myeloma treatment, or until death, but no longer than 3 years from the first study drug administration. Follow-up visits may be delayed for a maximum of 2 weeks after the normal visit window due to other reasons (e.g., logistical).

² The EOS visit will occur after at least 28 days after last study drug administration but should be performed before any new MM therapy starts, whichever occurs first. Subjects who complete Cycle 2 but do not receive additional cycles (Cycle 3+) have to perform Follow-up visit 1 and Follow-up visit 2 before EOS visit.

³ Including disease staging based on Durie-Salmon and International Staging System (ISS) criteria and documentation of immunoglobulin type.

⁴Before study drug administration.

⁵ Each cycle, starting with Cycle 3+: pre-dose at Day 1 (CxD1)

⁶ During Cycle 1, all subjects should be given premedication including an antipyretic (e.g., paracetamol) and a histamine H1 receptor blocker according to the local standard of care. In medically justified cases, the investigator may use other medications (e.g., steroids as per local standard but not exceeding 10 mg prednisolone equivalent), doses and/or formulations if this is documented thoroughly in the eCRF and the source data. If no infusion reaction occurs during Cycle 1, then premedication can be stopped at discretion of the investigator for subsequent treatment cycles. Otherwise, the premedication should be continued for subsequent administrations of MOR03087 as well.

⁷ Emergency Laboratory only to be taken if hematology/serum chemistry is not available prior to study drug administration

⁸ Sample to be taken and evaluated before study drug administration. On Day 1, additional sample (except AST and ALT) to be taken 2 hours after end of infusion.

⁹ β2-microglobulin to be measured at Screening only.

¹⁰ Pharmacokinetic sample to be taken predose and then at 1, 2, 4, 8, 14±2 (optional), 22±2, and 28±2 hours after start of first infusion.

¹¹ Pharmacokinetic sample to be taken predose and 2 hours after start of infusion.

¹² Pharmacokinetic sample during treatment Cycles 3+ to be taken every 2nd study drug administration (CxD15) predose and 2 hours after start of infusion.

¹³ Only if subject had no follow-up visit.

¹⁴ Samples for anti-MOR03087 antibodies will also be used to determine tetanus titer if sufficient quantities of serum are available.

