## 10.1.14 End of Study (EOS) Visit

The EOS visit will occur after confirmed disease progression, or after withdrawal from the study for other reasons, or at a maximum of 3 years from the first study drug administration. The EOS visit will occur at least 28 days after last study drug administration but should be performed before any new MM therapy starts, whichever occurs first.

At the EOS visit, the following will be obtained, performed, or assessed:

- Toxicity/AE assessment since the last visit
- Concomitant medications
- Karnofsky performance status
- Blood sample for hematology, serum chemistry, coagulation, βHCG pregnancy test for women of childbearing potential, MOR03087 pharmacokinetics (only if subject had no follow-up visit), endocrinology, anti-MOR03087 antibodies, B, T, and NK cells, serum M-protein, and serum FLCs
- Urine sample for urinalysis
- Sample from 24-hour urine for urine M-protein
- Bone skeletal survey by x-ray, CT, or MRI imaging (where medically indicated, as a regular assessment of standard of care in subjects with relapsed or refractory MM)
- Response assessment
- Physical examination (including basic neurological examination of general motor and sensory systems, mental status, cranial nerves, and coordination)
- Ocular examination by an ophthalmologist (including distance visual acuity, optical coherence tomography [if available], and ophthalmoscopy under full mydriasis [if optical coherence tomography is unavailable])
- Body weight
- Quality of life questionnaires (QLQ-MY20 and QLQ-C30)
- 12-Lead ECG
- Vital signs (blood pressure, pulse rate, respiratory rate, and body temperature)
- Documentation of subject's subsequent anti-myeloma therapy, as appropriate

For subjects receiving POM or LEN, the additional following will be obtained, performed, or assessed:

• Clinical review of signs/symptoms for possible VTEs in subjects treated with POM or LEN. Subjects who develop symptomatic deep vein thrombosis will be assessed and diagnosed objectively by Doppler ultrasonography or a comparable method per institution's standard of care. See Appendix 18.9 for deep vein thrombosis and pulmonary embolism diagnostic algorithms

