# **12 SAFETY MONITORING**

## 12.1 Adverse Event and Serious Adverse Event Recording and Reporting

All AEs/SAEs (except non-serious AEs for screening failures) that occur after the signing of informed consent and up to the End of Study visit (or up to 28 days after the last administration of study medication, whichever is earlier), will be recorded in the eCRF and in the subject's medical records, whether or not considered by the investigator to be related to the study drug. The SAEs should thereafter be recorded in the SAE Report Form and reported to the sponsor. All AEs/SAEs should be recorded using acceptable diagnoses, if possible. For screening failure subjects the non-serious AEs will not be recorded in the eCRF but only in the subject's medical records. The SAEs for screening failures will only be recorded until (including) the day when a subject is officially declared as screening failure.

Infusion reactions of grade 3 and higher, cytokine release syndrome, or allergic reaction to MOR03087, which are AEs of special interest in this study, should be reported along with their respective symptoms (e.g., urticaria, chills, and pyrexia for infusion reaction). If an AE has already been reported, it is not necessary to report each individual sign and symptom of that AE as a separate AE. For example, if myocardial infarction is reported as an AE, there is no need to report elevated creatine phosphokinase and abnormal ECG, or other related signs, symptoms, or laboratory values as separate AEs. However, if both occurred in isolation and myocardial infarction was not diagnosed, then each event would be reported as an AE.

Second primary malignancies will be monitored as events of special interest regardless of the treatment arm the subject is in. This includes any second primary malignancy, regardless of causal relationship to IP occurring at any time for the duration of the study. Events of second primary malignancy are to be reported using the SAE report form and must be considered an "Important Medical Event" if no other serious criteria apply. Documentation on the diagnosis of the second primary malignancy must be provided at the time of reporting (e.g., any confirmatory histology or cytology results, x-rays, CT scans, etc.).

The intensity of all AEs will be graded as mild, moderate, or severe using the following definitions:

- Mild: Tolerable
- Moderate: Interferes with normal activity

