Only patients experiencing a TEAE as mentioned above will be included in the summary table. The same table will be repeated for TEAEs related to MOR03087.

Exposure-adjusted incidence rate (EAIR) will be expressed as the number of patients experiencing an AE per patient-year (PY) of exposure to treatment and is derived as the number of patients with the event divided by the sum of all patient time at risk. Time at risk is the number of years from first treatment date to first event for patients experiencing a given event, or time on treatment in years (up to 28 days after the last study treatment) for patients who did not experience the event.

EAIR will be summarized by SOC and PT for the following:

- All TEAEs
- TEAEs related to MOR03087
- TEAEs related to any study drug
- TEAEs by grading according to NCI-CTCAE
- TEAEs leading to withdrawal of any study drug
- TEAEs that caused the subject to withdraw from the study
- SAEs

In the AE listings, AEs that started prior to the administration of any study drug will be flagged as pre-treatment AEs. Any AEs that start 28 days after the last study treatment, including all treatment cycles, will be flagged as post-treatment AEs.

A special AE summary listing displaying details of the event(s) captured on the eCRF in a compact format will be provided for

- DLTs
- Infusion reactions
- AEs leading to discontinuation on MOR03087
- AEs leading to discontinuation on Pomalidomide / Lenalidomide
- SAEs

Serious adverse event reconciliation will be performed by Data Management, Clinical Research, and Premier Research Drug Safety and Pharmacovigilance via data listings, as detailed in the SAE reconciliation plan.

The sponsor will describe other AEs of special interest (i.e. infusion reactions, cytokine release, allergic reaction to MOR03087, second primary malignancies and DLTs), in addition to those reported as SAEs.

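### SAP 10.2 does not end time at risk when adverse-event recording ends, so exposure-adjusted incidence rates can read low

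*Protocol*

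**What the plan says.** **The rate.** SAP 10.2 defines the EAIR as "the number of patients with the event divided by the sum of all patient time at risk". Subjects with the event contribute the time from first treatment to first event. The others contribute "time on treatment in years (up to 28 days after the last study treatment) for patients who did not experience the event". No shorter limit is given for an early EOS visit, death or the data cut-off. The same section closes the treatment-emergent window at the same 28 days.

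**The recording period.** Protocol 12.1 records adverse events "up to the End of Study visit (or up to 28 days after the last administration of study medication, whichever is earlier".

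**The EOS visit.** Protocol 10.1.14 says that the visit "will occur at least 28 days after last study drug administration but should be performed before any new MM therapy starts, whichever occurs first", and it expressly covers EOS "after withdrawal from the study for other reasons". Footnote 2 of Tables 1 and 2 in Section 7.1 repeats the interval: "The EOS visit will occur after at least 28 days after last study drug administration". Section 8.7.1, on subjects who withdraw or are withdrawn, says instead: "A complete final evaluation at the time of the subject's withdrawal (End of Study visit) should be made".

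**The concern.** An incidence rate is unbiased only if a subject's clock stops when events can no longer be captured. Under Section 12.1 an EOS visit held 3 or 14 days after the last dose closes the record on that day, yet the SAP clock runs on to day 28. The extra days can add nothing to the numerator and always add to the denominator, so the rate is pulled down.

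There are two routes to an early EOS: the visit is moved ahead of new myeloma therapy, or it is held at withdrawal under Section 8.7.1. The first is foreseeable in relapsed or refractory myeloma. EAIRs are planned by system organ class and preferred term for seven categories, including serious events and events leading to withdrawal. They will be read across parts whose exposure may differ. A group with more early departures would look somewhat safer per patient-year than it was.

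**Working it through.** **Which dates apply.** For a subject who leaves the study within 28 days of the last dose and starts no new myeloma therapy, Section 8.7.1 puts EOS at withdrawal, while Section 10.1.14 and footnote 2 put it at 28 days or later. Both cannot be met. For a subject who starts new therapy within 28 days, the two sections need not conflict, but EOS is still early. Section 8.7.1 continues to monitor an adverse event that caused the withdrawal; that does not reopen the recording of new events.

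**No plan figure to reproduce.** The documents give no EAIR, no withdrawal frequency and no expected treatment duration. Every size below rests on assumed values.

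**One subject without the event.** Let the last dose be on Day *D* and EOS *g* days later, with *g* < 28.

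- Days on which events can be recorded: *D* + *g*
- Days counted by the SAP: *D* + 28
- Shortfall: 1 − (*D* + *g*)/(*D* + 28)

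| Last dose | EOS after last dose | Recordable | Counted | Shortfall |
|---|---|---|---|---|
| Day 22 | 3 days | 25 | 50 | 50% |
| Day 22 | 14 days | 36 | 50 | 28% |
| Day 106 | 3 days | 109 | 134 | 19% |
| Day 106 | 14 days | 120 | 134 | 10% |

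These are single-subject ratios, not EAIRs.

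**A group of nine.** Nine is the minimum recommended-dose group in Protocol 15.9 and SAP 5. Assume that three subjects have the first pattern in the table and that six contribute 134 days under either rule.

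- SAP denominator: 3 × 50 + 6 × 134 = 954 days
- Recordable days: 3 × 25 + 6 × 134 = 879 days
- Inflation: 954/879 = 1.085, or 8.5%
- EAIR: 1 − 879/954 = 7.9% low, since the event count cancels

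**Dependence on treatment length.** Assume nine subjects: three with the event at Day 14 (3 × 14 = 42 days) and six without it, of whom three have EOS 7 days after the last dose. All six are treated for *T* days. Counted time is 42 + 6(*T* + 28). Recordable time is 42 + 3(*T* + 28) + 3(*T* + 7). The excess is always 63 days. Rates use 365.25 days per year.

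| *T* (days) | Counted | Recordable | EAIR per SAP | EAIR on recordable time | Low by |
|---|---|---|---|---|---|
| 28 | 378 | 315 | 2.90 | 3.48 | 16.7% |
| 84 | 714 | 651 | 1.54 | 1.68 | 8.8% |
| 168 | 1218 | 1155 | 0.90 | 0.95 | 5.2% |
| 336 | 2226 | 2163 | 0.49 | 0.51 | 2.8% |

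Keeping three events at Day 14 but varying the number of early EOS visits (1, 3 or 6), their timing (0, 7 or 14 days) and *T*, the EAIR is 0.6% to 44.4% low. A constant-hazard check (0.5 or 2.0 events per patient-year, EOS at 7 days in 10% to 50% of subjects, *T* from 28 to 168 days) gives an expected EAIR 0.7% to 18.5% below the true rate. The direction is downward whenever *g* < 28.

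**The case against.** The strongest reply is that *up to* in the SAP sets a ceiling, so a programmer could stop the clock sooner. This fails as a defence: no rule says when to stop sooner, and the treatment-emergent definition uses the same 28 days as a plain end point. By contrast, SAP 7.3 states censoring for antibody development, response duration and progression.

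A second reply stands in part: the affected group is narrow. Subjects whose study drug the investigator stops for illness or adverse events may complete the follow-up visits (8.7.1). Those stopped for a long delay go to the first follow-up visit (8.6), and those who stop without progression are seen four weeks after the last dose (10.1.12). Footnote 2 also sends subjects who complete Cycle 2 and receive no further cycle through two follow-up visits before EOS. A last dose on Day 50 is therefore not a safe example, unless Section 8.7.1 overrides the footnote.

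A reader might also infer more than the documents support:

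- **That the primary adverse-event endpoint is biased by this rule.** Protocol 15.7.2 and SAP 10.2 summarise it as numbers and percentages of subjects, with no person-time. An early EOS can leave later events uncaptured there too, but that is not the denominator error.
- **That dose decisions are affected.** These rest on first-cycle dose-limiting toxicities and review by the data monitoring committee, and no formal comparison of EAIRs is planned.
- **That time after the data cut-off will be counted.** SAP 4.2 limits the analysis to data available up to the cut-off. The EAIR rule should say so, but the documents do not show that such time would enter.
- **That Section 8.7.1 is the root of the error.** Correcting it alone leaves the new-therapy route open.

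**Conclusion.** The point holds for the EAIRs. As written, SAP 10.2 counts person-time after adverse-event recording has closed, for every subject without the event whose EOS falls before 28 days. The direction is certain; the size is not, because it depends on how many subjects leave early, how soon EOS follows, and how long they were treated. Under the assumed Cycle 1 pattern above, one third of a nine-subject group leaving early makes the EAIR about 8% low. The effect fades to a few percent with long treatment and grows if most of a group leaves in the first cycle. It deserves correction before the analysis is programmed, as a defect in a supplementary safety summary. The inconsistency in EOS timing is a separate, smaller matter that needs its own reconciliation.

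**What to change.** 1. **SAP 10.2.** State that time at risk ends at the earliest of: first event, 28 days after last study treatment, the EOS visit or last adverse-event assessment, death, and the data cut-off. This corrects the EAIR denominator however the protocol is reconciled.
2. **Protocol.** Reconcile Section 8.7.1 with Section 10.1.14, footnote 2 of Tables 1 and 2, and Section 12.1, so that they agree on when EOS takes place for a withdrawn subject and when recording closes. Which timing to adopt is for the sponsor.

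The cost is one sentence in the SAP and a clarification in the protocol. The SAP change needs no new data collection. Its one visible effect is that EAIRs become slightly higher.
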